# PPD

AE START DATE	AE STOP DATE	RULE for TEAE definition	RULE for "Treatment"/"Follow-up" study period definition for TEAE summaries
	Partial	Impute stop date as latest possible date (i.e. last day of month if day unknown or 31st December if day and month are unknown), then: If AE stop date < IMP start date, then not TEAE If AE stop date $\geq$ IMP start date, then TEAE	
	Missing	Assumed TEAE	
Missing	Known	If AE stop date < IMP start date, then not TEAE If AE stop date $\geq$ IMP start date, then TEAE	If TEAE, then Treatment study period for TEAE occurrence.
	Partial	Impute AE stop date as latest possible date (i.e. last day of month if day unknown or 31st December if day and month are unknown), then: If AE stop date < IMP start date, then not TEAE If AE stop date $\geq$ IMP start date, then TEAE	
	Missing	Assumed TEAE	

NOTE: \* Assignment to "Treatment" or "Follow-up" study period is applicable only for TEAEs.

# PPD

Table 6: Algorithm for Prior/Concomitant medications

• MEDICATION DATE	START	• MEDICATION STOP DATE	• RULE for prior or concomitant categorization
Known	Known		If medication stop date < date of informed consent, assign as prior If medication stop date $\geq$ date of informed consent, assign as concomitant
	Partial		Impute medication stop date as latest possible date (i.e. last day of month if day unknown or 31 st December if day and month are unknown), then: If medication stop date < date of informed consent, assign as prior If medication stop date $\geq$ date of informed consent, assign as concomitant
	Missing		Assign as concomitant
Partial or Missing	Known		If medication stop date < date of informed consent, assign as prior If medication stop date $\geq$ date of informed consent, assign as concomitant
	Partial		Impute medication stop date as latest possible date (i.e. last day of month if day unknown or 31 st December if day and month are unknown), then: If medication stop date < date of informed consent, assign as prior If medication stop date $\geq$ date of informed consent, assign as concomitant
	Missing		Assign as concomitant

# PPD

## 10. Tables, Figures and Listings

### 10.1 Output conventions

- Each Table, Listing and Figure (TFL) should be numbered, if applicable, following the ICH E3 guideline.
- All tables/figures/listings will be presented in landscape format.
- The standard font size is 9 points “Courier New” for all tables. Listings will be presented with an 8 or 7 points Arial.
- Titles will be center-aligned; footnotes will be left-aligned.
- Each table/figure/listing will have 2 titles:
  - The 1st title will be the table/figure/listing number with the description of the table/figure/listing;
  - The 2nd title will be a description of the study set presented in the table/figure/listing.
- Some tables will have a third title (before 2nd title) with a description of the statistical method used in those tables.
- Any footnote added to explain the table/listing/figure contents will be presented in the following format:
  - Note 1: ...
  - Note 2: ...
  - Note 3: ...
- In the tables, listing and figures the treatment under comparison will be labelled as “Ladarixin” and “Placebo”
- Missing descriptive statistics or p-values which cannot be estimated are reported as “-”.
- The last two footnotes of each table/figure will be footers indicating:
  - the reference listing of the data;
  - the program name, the date and time of generation and the SAS® version used.
- Unless otherwise stated, listings will be presented by randomised treatment, and sorted by the treatment group, patient number, and visit.
- In all the listings on safety variables, a column with a flag (\$) for treatment misallocation will identify the treatment misallocations.
- The derived variables will be identified in the listings with a flag (\*).
- In general, dates will be presented on listings in the format ddmmmyyyy (date9.) and time in the format hh:mm (time5.). In case of partial dates or times, missing information will be replaced by dashes.
- Numeric variables will be listed generally with the same number of decimal places as in the actual data; units will be presented enclosed in square brackets ([ ]), when appropriate.

## 12. Appendices

### 12.1 R code for CGM

R code	Notes
<pre>Cgmvariables_mod <- function(inputdirectory,   outputdirectory = tempdir(),   outputname = "Dexcom",   customintervals = list(c(.)),   aboveexcursionlength = 35,   belowexcursionlength = 10,   magedef = "1sd",   congan = 1,   daystart = 0,   dayend = 24,   id_filename = F,   format = "rows",   printname = F) {  # Read in data, create results dataframe. The dataframe has one column for each # file in the input directory, and is designed to be uploaded to REDCap. files <- base::list.files(path = inputdirectory, full.names = TRUE) cgmupload <-   base::as.data.frame(base::matrix(nrow = 0, ncol = base::length(files))) base::colnames(cgmupload) <- base::rep("Record", base::length(files)) # Define the order in which lubridate parses dates. dateparseorder <- c("mdy HM", "mdy HMS", "mdY HM", "mdY HMS", "dmy HM", "dmy HMS",   "dmY HM", "dmY HMS", "Ymd HM", "Ymd HMS", "ymd HM", "ymd HMS",   "Ydm HM", "Ydm HMS", "ydm HM", "ydm HMS") allhours <- 0:23 # Iterate through the input directory and calculate CGM variables for each file. # The cgmvariables() function only works on CSV files that have been cleaned by # cleandata(), or that have been manually edited and fit the format of # cleandata() output. for (f in 1:base::length(files)) {   # Basic variables   table <- utils::read.csv(files[f], stringsAsFactors = FALSE, na.strings = c("NA", ""))   # Remove duplicates   if(id_filename == F) {     table\$subjectid <- table\$subjectid[1]   } else {     table\$subjectid[1] <- sub("*.csv", "", basename(files[f]))   }   table <- unique(table)   # Print name</pre>	Minor manipulation of the imported files may be done by data management and programming in order to make the files readable by the algorithm.

# PPD

R code	Notes
<pre> if(printname == T) {   print(basename(files[f])) }  # Column names to lower case colnames(table) = tolower(colnames(table)) cgmupload["subject_id",f] <- table\$subjectid[1] # Format columns. table\$timestamp <-   base::as.POSIXct(lubridate::parse_date_time(table\$timestamp,   dateparseorder,tz = "UTC")) table\$sensorglucose <- suppressWarnings(base::as.numeric(table\$sensorglucose)) interval <- pracma::Mode(base::diff(base::as.numeric(table\$timestamp))) interval <- base::abs(interval) cgmupload["date_cgm_placement", f] <-   base::as.character(min(table\$timestamp,na.rm = T))  totaltime <-   base::as.numeric(base::difftime(base::max(table\$timestamp, na.rm = T),                                    base::min(table\$timestamp,na.rm = T),                                    units = "secs")) cgmupload["percent_cgm_wear",f] <-  base::floor(((base::length(which(!is.na(table\$sensorglucose)))/(totaltime/interval))*100)) cgmupload["num_days_good_data",f] <-   base::round(base::length(which(!is.na(table\$sensorglucose)))/(86400/interval))  table <- table[!is.na(table\$timestamp) & !is.na(table\$sensorglucose),]  cgmupload["total_sensor_readings",f] <-   base::as.numeric(base::length(base::which(!is.na(table\$sensorglucose)))) cgmupload["average_sensor",f] <-   base::mean(table\$sensorglucose[base::which(!is.na(table\$sensorglucose))],na.rm = T) cgmupload["estimated_a1c",f] <-   base::round((46.7 + (base::mean(table\$sensorglucose[   base::which(!is.na(table\$sensorglucose))])) / 28.7,digits = 1) cgmupload["gmi",f] <- base::round(3.31 + (0.02392 * base::mean(table\$sensorglucose[   base::which(!is.na(table\$sensorglucose))])), digits = 1) cgmupload["q1_sensor",f] <-   base::as.numeric(base::summary(table\$sensorglucose[   base::which(!is.na(table\$sensorglucose))])[2]) cgmupload["median_sensor",f] <-   base::as.numeric(base::summary(table\$sensorglucose[   base::which(!is.na(table\$sensorglucose))])[3]) cgmupload["q3_sensor",f] <-   base::as.numeric(base::summary(table\$sensorglucose[   base::which(!is.na(table\$sensorglucose))])[5]) </pre>	

# PPD

R code	Notes
<pre> cgmupload["standard_deviation",f] <-   stats::sd(table\$sensorglucose[base::which(!is.na(table\$sensorglucose))])  cgmupload["cv",f] <-   (stats::sd(table\$sensorglucose[base::which(!is.na(table\$sensorglucose))])/   base::mean(table\$sensorglucose[base::which(!is.na(table\$sensorglucose))]))  cgmupload["min_sensor",f] <-   base::min(table\$sensorglucose[base::which(!is.na(table\$sensorglucose))])  cgmupload["max_sensor",f] <-   base::max(table\$sensorglucose[base::which(!is.na(table\$sensorglucose))])  # Excursions over 120 calculations.  BGover120 <-   base::as.numeric(table\$sensorglucose[base::which(!is.na(     table\$sensorglucose))],length = 1) BGover120[BGover120 < 120] <- 0 BGover120[BGover120 >= 120] <- 1 BG120.rle <- base::rle(BGover120) excursions120 <-   base::as.numeric(BG120.rle\$lengths[base::which(BG120.rle\$values == 1)])   cgmupload["excursions_over_120",f] <-   base::length(base::which(excursions120 >     ((aboveexcursionlength * 60)/interval))) cgmupload["min_spent_over_120",f] <- base::sum(BGover120) * (interval/60) cgmupload["percent_time_over_120",f] <-   ((base::sum(BGover120) * (interval/60))/   (base::length(table\$sensorglucose) * (interval/60))) * 100  # Over 140.  BGover140 <-   base::as.numeric(table\$sensorglucose[base::which(!is.na(     table\$sensorglucose))],length = 1) BGover140[BGover140 < 140] <- 0 BGover140[BGover140 >= 140] <- 1 BG140.rle <- base::rle(BGover140) excursions140 <-   base::as.numeric(BG140.rle\$lengths[base::which(BG140.rle\$values == 1)])   cgmupload["excursions_over_140",f] <-   base::length(base::which(excursions140 >     ((aboveexcursionlength * 60)/interval))) cgmupload["min_spent_over_140",f] <- base::sum(BGover140) * (interval/60) cgmupload["percent_time_over_140",f] <-   ((base::sum(BGover140) * (interval/60))/   (base::length(table\$sensorglucose) * (interval/60))) * 100  # Over 180.  BGover180 <- </pre>	

# PPD

R code	Notes
<pre> base::as.numeric(table\$sensorglucose[base::which(!is.na(   table\$sensorglucose))],length = 1) BGover180[BGover180 < 180] <- 0 BGover180[BGover180 >= 180] <- 1 BG180.rle <- base::rle(BGover180) excursions180 <-   base::as.numeric(BG180.rle\$lengths[base::which(BG180.rle\$values == 1)])   cgmupload["excursions_over_180",f] <-   base::length(base::which(excursions180 >     ((aboveexcursionlength * 60)/interval))) cgmupload["min_spent_over_180",f] <- base::sum(BGover180) * (interval/60) cgmupload["percent_time_over_180",f] <-   ((base::sum(BGover180) * (interval/60))/   (base::length(table\$sensorglucose) * (interval/60))) * 100  # Over 200. BGover200 <-   base::as.numeric(table\$sensorglucose[base::which(!is.na(     table\$sensorglucose))],length = 1) BGover200[BGover200 < 200] <- 0 BGover200[BGover200 >= 200] <- 1 BG200.rle <- base::rle(BGover200) excursions200 <-   base::as.numeric(BG200.rle\$lengths[base::which(BG200.rle\$values == 1)])   cgmupload["excursions_over_200",f] <-   base::length(base::which(excursions200 >     ((aboveexcursionlength * 60)/interval))) cgmupload["min_spent_over_200",f] <- base::sum(BGover200) * (interval/60) cgmupload["percent_time_over_200",f] <-   ((base::sum(BGover200) * (interval/60))/   (base::length(table\$sensorglucose) * (interval/60))) * 100  cgmupload["avg_excur_over_140_per_day",f] <-   as.numeric(cgmupload["excursions_over_140",f])/   as.numeric(cgmupload["num_days_good_data",f]) cgmupload["avg_excur_over_200_per_day",f] <-   as.numeric(cgmupload["excursions_over_200",f])/   as.numeric(cgmupload["num_days_good_data",f])  # Over 250. BGover250 <-   base::as.numeric(table\$sensorglucose[base::which(!is.na(     table\$sensorglucose))],length = 1) BGover250[BGover250 < 250] <- 0 BGover250[BGover250 >= 250] <- 1 BG250.rle <- base::rle(BGover250) </pre>	

# PPD

R code	Notes
<pre> excursions250 <-   base::as.numeric(BG250.rle\$lengths[base::which(BG250.rle\$values == 1)])   cgmupload["excursions_over_250",f] <-   base::length(base::which(excursions250 >     ((aboveexcursionlength * 60)/interval))) cgmupload["min_spent_over_250",f] <- base::sum(BGover250) * (interval/60) cgmupload["percent_time_over_250",f] <-   ((base::sum(BGover250) * (interval/60))/   (base::length(table\$sensorglucose) * (interval/60))) * 100  # Under 54. BGunder54 <-   base::as.numeric(table\$sensorglucose[base::which(!is.na(     table\$sensorglucose))],length = 1) BGunder54[BGunder54 <= 54] <- 1 BGunder54[BGunder54 > 54] <- 0 BG54.rle <- base::rle(BGunder54) excursions54 <-   base::as.numeric(BG54.rle\$lengths[base::which(BG54.rle\$values == 1)])   cgmupload["excursions_under_54",f] <-   base::length(base::which(excursions54 >     ((belowexcursionlength * 60)/interval))) cgmupload["min_spent_under_54",f] <- base::sum(BGunder54) * (interval/60) cgmupload["percent_time_under_54",f] <-   ((base::sum(BGunder54) * (interval/60))/   (base::length(table\$sensorglucose) * (interval/60))) * 100  # Under 60. BGunder60 <-   base::as.numeric(table\$sensorglucose[base::which(!is.na(     table\$sensorglucose))],length = 1) BGunder60[BGunder60 <= 60] <- 1 BGunder60[BGunder60 > 60] <- 0 BG60.rle <- base::rle(BGunder60) excursions60 <-   base::as.numeric(BG60.rle\$lengths[base::which(BG60.rle\$values == 1)])   cgmupload["excursions_under_60",f] <-   base::length(base::which(excursions60 >     ((belowexcursionlength * 60)/interval))) cgmupload["min_spent_under_60",f] <- base::sum(BGunder60) * (interval/60) cgmupload["percent_time_under_60",f] <-   ((base::sum(BGunder60) * (interval/60))/   (base::length(table\$sensorglucose) * (interval/60))) * 100  # Under 70. </pre>	

# PPD

R code	Notes
<pre> BGunder70 <-   base::as.numeric(table\$sensorglucose[base::which(!is.na(table\$sensorglucose))],   length = 1) BGunder70[BGunder70 <= 70] <- 1 BGunder70[BGunder70 > 70] <- 0 BG70.rle <- base::rle(BGunder70) excursions70 <-   base::as.numeric(BG70.rle\$lengths[base::which(BG70.rle\$values == 1)])  cgmupload["excursions_under_70",f] <-   base::length(base::which(excursions70 >     ((belowexcursionlength * 60)/interval))) cgmupload["min_spent_under_70",f] <- base::sum(BGunder70) * (interval/60) cgmupload["percent_time_under_70",f] <-   ((base::sum(BGunder70) * (interval/60))/   (base::length(table\$sensorglucose) * (interval/60))) * 100  # Time in range. BGinrange <-   base::as.numeric(table\$sensorglucose[base::which(!is.na(table\$sensorglucose))],   length = 1) BGinrange <- ifelse(BGinrange %in% 70:180, 1,0) cgmupload["min_spent_70_180",f] <- base::sum(BGinrange) * (interval/60) cgmupload["percent_time_70_180",f] <-   ((base::sum(BGinrange) * (interval/60))/   (base::length(table\$sensorglucose) * (interval/60))) * 100  # Custom intervals if(!is.null(customintervals[[1]])) {   lows <- unlist(lapply(customintervals, '[' , 1))   highs <- unlist(lapply(customintervals, '[' , 2))   for (r in 1:length(customintervals)) {     # Range     BGinrange <-       base::as.numeric(table\$sensorglucose[base::which(!is.na(table\$sensorglucose))],       length = 1)     BGinrange <- ifelse(BGinrange %in% lows[r]:highs[r], 1,0)     minname <- paste0("min_spent_",lows[r],"_",highs[r])     cgmupload[minname,f] <- base::sum(BGinrange) * (interval/60)     percname <- paste0("percent_time_",lows[r],"_",highs[r])     cgmupload[percname,f] <-       ((base::sum(BGinrange) * (interval/60))/       (base::length(table\$sensorglucose) * (interval/60))) * 100   # Below   BGunder <-     base::as.numeric(table\$sensorglucose[base::which(!is.na(table\$sensorglucose))],     length = 1)   BGunder[BGunder <= lows[r]] <- 1 } </pre>	

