### 14.3.4. Handling of CGM device

The Dexcom G6 Continuous Glucose Monitoring System (Dexcom G6 System) will be used to perform a CGM. CGM measures the subject's interstitial glucose level using electrodes that measure an electric signal produced by glucose oxidase reaction. The system records data approximately every 5 minutes. CGM will be used periodically to measure the subject's interstitial glucose level according to the schedule presented in study flow chart/time and event schedule. A CGM sensor will be inserted subcutaneously at the site 14-10 days before the concerned visits (Baseline, Month 6, 12, 18) and removed during the day of the concerned visit, as per Study Flowchart (see Appendix 14.2).

CGM sensor implantation can occur at Screening Visit and Week 23 Visit if the visit is scheduled 14-10 days before Baseline and before Week 26 respectively. In addition, sites should upload the sensor data to check subject's compliance with wearing the device. The sensor requires at least one SMBG value to be entered every 12 hours for calibration during use. At a minimum, a SMBG value obtained in the morning (e.g. fasting or pre-breakfast measurement) should be entered, as well as a value in the evening (e.g. pre- or post-dinner measurement). Subjects may be instructed to use results from the 4 daily SMBG measures to fulfill these criteria. Every fourteen/ten (10/14) days the sensor needs to be replaced and subjects can return to the site for assistance on this if needed. If the subject needs assistance with sensor replacement, an ad-hoc visit should be performed, if this occurs a data upload is also recommended at this time. If subjects opt to perform sensor replacement at home sites should call subject 7 days after insertion as a reminder.

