### 3.6.2 Secondary efficacy endpoints

The secondary efficacy endpoints are the following:

- Proportion of patients with HbA1c <7% and daily insulin requirement <0.50 IU/Kg/day at Month 6 and 18;
- Proportion of patients with a reduction in HbA1c > 0.5% from baseline and daily insulin requirement <0.50 IU/Kg/day at Month 6, 12, and 18;
- 2-hour Area Under the Curve (AUC) of C-peptide response to the Mixed Meal Tolerance Test (MMTT) at Month 6, 12, and 18;
- Time in range (TIR) by Continuous Glucose Monitoring (CGM) at Month 6, 12, and 18;
- HbA1c levels at Month 6, 12, and 18;
- Proportion of patients with HbA1c <7% who did not experience severe hypoglycaemic events during treatment at Month 6, 12, and 18;
- Additional Glucose Variability Indices derived from CGM at Month 6, 12, and 18;
- Number of self-reported episodes of severe hypoglycaemia at Month 6, 12, and 18;
- Average (previous 3 days) daily insulin requirements (IU/kg/day) at Month 6, 12, and 18;
- Estimated Glucose Disposal Rate (eGDR) at Month 6, 12, and 18;

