## 9.2 CGM value derivation

The Dexcom G6 Continuous Glucose Monitoring System (Dexcom G6 System) will be used to perform CGM during the study. Dexcom G6 System uses proprietary algorithms to create fully customizable reports and summary measures for patients and clinicians. These reports will not be used during the trial given the fully customizable features. Instead, in order to standardize the summary statistics from each patient, the *cgmanalysis* package written entirely in the statistical programming language R (R Foundation for Statistical Computing, Vienna, Austria) will be used given its compatibility with raw data structure coming from Dexcom G6 System.

Gaps in glucose data shorter or equal than 30 minutes will be imputed using linear interpolation. The *cgmanalysis* package cleandata function will be used.

After filling eventual gaps in the glucose data, the following requirements should be met for a visit in order to be considered eligible for analysis:

- a total of at least 7 days of valid CGM recordings will be required for a visit to be used for analysis (by study protocol, at least 10 days before each scheduled visit the CGM sensor should be positioned):
  - *cgmanalysis*: num\_days\_good\_data  $\geq 7$ ;
- the number of sensor readings as a percentage of the number of potential readings (given time worn) has to be greater than 80%:
  - *cgmanalysis*: percent\_cgm\_wear  $> 80\%$ .

The *cgmanalysis* package *cgmvariables* function will be used for the CGM parameters (sections 7.2.1.4 and 7.2.1.7). The package has been modified in order to perform additional simultaneous analyses (see Appendix 12.1 for the entire R code). Table 5 reports the correspondence between required endpoint and *cgmvariables* outcomes.

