**Table 4: Variable in cgmanalysis**

Endpoint	Variable in cgmanalysis	Unit
TIR	percent_time_70_180	%
Glucose AUC outside the target range of 70/180 mg/dL	average_auc_70 + average_auc_180	mg/dL/min
MAGE (1 SD)	r_mage	mg/dL
CONGA-1, CONGA-2 and CONGA-4	conga_1, conga_2, conga_4	mg/dL
MODD	modd	mg/dL
Mean daily blood glucose	average_sensor	mg/dL
SD	standard_deviation	mg/dL
2h-PPG	average_auc_per_day*	mg/dL

*\*raw data must be filtered with observations  $\leq$  120 minutes from meals (eDiary)*

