# PPD

R code	Notes
<pre> rl <- table\$rBG[base::which(table\$gluctransform < 0)] rh <- table\$rBG[base::which(table\$gluctransform > 0)] cgmupload["lbgi",f] <- base::mean(stats::na.omit(rl)) cgmupload["hbgi",f] <- base::mean(stats::na.omit(rh)) }  # Write file. cgmupload <-   base::cbind("Variable / Field Name" = rownames(cgmupload),cgmupload) if (format == "rows") {   cgmupload <- base::as.data.frame(base::t(cgmupload))   cgmupload <- cgmupload[-1,] } filename <- base::paste(outputdirectory,"/",outputname,".csv",sep = "") utils::write.csv(cgmupload, file = filename, row.names = FALSE,na = "") } </pre>	
<pre> library(cgmanalysis) library(stringi) library(base)  cleandata(   inputdirectory = "path\\to\\data",   outputdirectory = "path\\to\\cleaned_data",   removegaps = FALSE, gapfill = TRUE, maximumgap = 30)  cgmvariables_mod(   inputdirectory = "path\\to\\cleaned_data",   outputdirectory = "path\\to\\output",   outputname = "Dexcom",   customintervals = list(c(250,400)),   aboveexcursionlength = 35,   belowexcursionlength = 10,   magedef = "1sd",   congan = 1,   daystart = 0,   dayend = 24,   id_filename = F,   format = "rows",   printname = F ) </pre>	
Cleandata will fill in gaps shorter than 30 minutes but will not remove the 24-hour chunks containing larger gaps.
 
Parameters customintervals, aboveexcursionlength, belowexcursionlength, congan, daystart, dayend will not be used.

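### The SAP's time-in-range code accepts only whole-number glucose values, so fractional gap-filled readings that are in range are dropped from the numerator and TIR is understated, unless the unprinted cleaning step rounds

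*SAP*

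**What the plan says.** TIR is a secondary efficacy endpoint in SAP Section 3.6.2: "Time in range (TIR) by Continuous Glucose Monitoring (CGM) at Month 6, 12, and 18". Table 4 takes it from the code variable "percent_time_70_180", in percent.

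Three steps produce that variable:

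- **Gap filling.** Section 9.2 states: "Gaps in glucose data shorter or equal than 30 minutes will be imputed using linear interpolation". The call at the end of Appendix 12.1 switches this on with "removegaps = FALSE, gapfill = TRUE, maximumgap = 30" before any CGM variable is computed.
- **Classification.** The overall TIR line in Appendix 12.1 is "ifelse(BGinrange %in% 70:180, 1,0".
- **Percentage.** The numerator is "base::sum(BGinrange) * (interval/60", that is, the flagged readings in minutes. The denominator is the time represented by all non-missing readings, including filled ones.

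The printed code converts sensor glucose to numeric and does not round it. It does round other quantities, such as estimated A1c and days of good data.

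Section 7.2.1.4 summarises TIR and its change from baseline and compares arms by t-test or Mann-Whitney test. Section 7.2 plots the means and marks significant p-values. Sections 4.8 and 7 state that all analyses are descriptive after the early closure.

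**The concern.** In R, `70:180` is a list of 111 whole numbers and `%in%` tests exact membership. A reading of 122.5 mg/dL is plainly within 70 to 180, yet the line scores it 0. The overall time-above and time-below lines use inequalities, so the same reading is not above, not below and not in range. No sensible definition of TIR intends that.

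The SAP's own gap filling is what creates fractional values. The amount of TIR lost therefore follows signal loss, not glycaemia. A patient whose sensor drops out more often would appear less well controlled than one with the same glucose and a complete trace. Dropout can also differ between a patient's visits, which would add non-glycaemic variation to change from baseline in a trial that is already smaller than planned.

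The eligibility rule for a visit does not limit this. The wear requirement ("given time worn) has to be greater than 80"%) is applied after filling, so filled readings count as wear, and no rule caps the share of readings that are interpolated.

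**Working it through.** The plan gives no figure for this point, so there is nothing of its own to reproduce. The check has four steps.

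**Inputs from the documents.** The classification line, the gap-filling rule and the denominator are as described above. Protocol Appendix 14.3.4 gives the recording interval: "The system records data approximately every 5 minutes". A fillable gap therefore holds about 1 to 5 missing readings, at most 6.

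**Inputs assumed.** Raw readings are whole mg/dL. `cleandata` does not round. True TIR is about 67%. The share of filled readings, f, is 1% to 10%.

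**1. The rule on a worked gap.** Take readings of 120 and 130 mg/dL with three missing between them. Linear interpolation gives 122.5, 125.0 and 127.5. Run in R, the printed line scores these 0, 1, 0. An inequality scores them 1, 1, 1.

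**2. Share of filled values that are fractional.** With k missing readings between whole-number endpoints whose difference is spread evenly modulo k+1:

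p(k) = 1 - [average over j = 1..k of gcd(j, k+1)] / (k+1)

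| k | 1 | 2 | 3 | 4 | 5 | 6 |
|---|---|---|---|---|---|---|
| p(k) | 50% | 67% | 67% | 80% | 70% | 86% |

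For k = 5, the gcd values are 1, 2, 3, 2, 1, with average 1.8, so p = 1 - 1.8/6 = 0.70. If gaps of 1 to 5 readings are equally frequent, weighting by readings gives (1×0.50 + 2×0.667 + 3×0.667 + 4×0.80 + 5×0.70)/15 = 0.70.

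**3. Size of the error.** Approximately, error = -f × p × TIR. With p = 0.70 and TIR = 67%:

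- f = 1%: -0.01 × 0.70 × 67 = -0.47 points
- f = 2%: -0.94 points
- f = 5%: -2.35 points
- f = 10%: -4.69 points

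Simulated ten-day, 5-minute whole-number traces (mean 150, SD 50 mg/dL, gaps of 1 to 5 readings, linear fill) agree: about -0.5, -1.0, -2.4 and -4.7 points. About 65–70% of in-range filled readings were lost. With single-reading gaps only, about half were lost, and the errors were -0.3, -1.7 and -3.4 points at 1%, 5% and 10% filled. No out-of-range reading was ever scored as in range, so the error has one direction.

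**4. Effect on the arm comparison.** If f and p are the same in both arms, each arm's TIR is multiplied by (1 - f × p). At f = 5% that is 1 - 0.05 × 0.70 = 0.965, so a true difference shrinks by 3.5% of itself and a null difference stays null. Only unequal gap frequency would create a difference where none exists.

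**The case against.** The strongest objection is that the gap filling happens in code the reader cannot see. `cleandata` is called but not printed. If it returns whole numbers, the membership test is harmless. That condition stands and belongs in the conclusion. It does not make the line correct: nothing in the SAP promises rounding, and a range rule should not depend on an unstated property of an earlier step.

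The size is also unknown. The documents give no fill share. With few short gaps the loss is well under one point, and it is smaller still where glucose is flat. The rows for 5% and 10% illustrate; they do not predict.

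A reader might infer four stronger things, which the documents do not support:

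- **That every patient's TIR is too low.** A file with no filled gaps, or only whole-number fills, is unaffected.
- **That the treatment comparison is biased.** The rule does not depend on arm, CGM data are blinded during recording (Protocol Appendix 14.3.4), and nothing suggests that gaps differ by arm.
- **That TIR could collapse through unit conversion from mmol/L.** Table 4 gives the CGM glucose indices in mg/dL, and neither document mentions CGM files in mmol/L.
- **That shares not totalling 100% prove this fault.** The overall below and above lines use `<= 70` and `>= 180`, so readings of exactly 70 or 180 are counted twice. In simulation the shares total about 100.9% even with a corrected TIR line.

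The day, night and custom-interval lines contain the same test but feed no endpoint in Table 4.

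**Conclusion.** The overall TIR line is wrong as written for any fractional value. Provided that `cleandata` does not round, TIR is understated, never overstated, in each file with fractional filled readings whose true value is in range. With whole-number raw readings, about half of the in-range filled values are lost for single-reading gaps, and about 65–70% for a mix of 1 to 5.

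At an assumed true TIR of about 67%, this costs from about half a point at 1% filled to nearly five points at 10%. The consequence is a lower absolute TIR and added noise in change from baseline. The arm comparison is distorted only if gap frequency or true TIR differs between arms.

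TIR is one of ten secondary endpoints, and no formal conclusion rests on it now that the analyses are descriptive. It is still tabulated, tested and plotted, so the correction is worth making, but it does not call the trial's main result into question.

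**What to change.** In the overall TIR line of SAP Appendix 12.1, use `ifelse(BGinrange >= 70 & BGinrange <= 180, 1, 0)`. The day, night and custom-interval lines can be changed in the same way for consistency, though no listed endpoint needs it.

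Re-run the function on the cleaned files. For each file, confirm that TIR plus time strictly below 70 plus time strictly above 180 equals 100%. The printed overall under-70 and over-180 variables cannot serve for this check unchanged, because they include the boundary values.

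It would also help to report the share of filled readings per visit and to state whether `cleandata` rounds. A reader could then see how much the change mattered.

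The cost is one edited line, a short check and a re-run. No new data are needed.
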